 - Differences in prolonged pain defined as postoperative pain more than 3 months after surgery in the NFIR questionnaire or having had treatment for pain caused by the surgery, e.g removal of the sling or part of the sling. Patients having persistent ongoing pain will further be asked to answer a newly developed non-validated NFIR pain questionnaire (40).

2) Long-term objective outcomes

[figure not shown]
Study population: The 318 women having been treated with the currently most used shorter sling (TVT-A) at Akershus University Hospital between 2016 and 2020 will be invited to a physical follow-up where they will undergo a clinical examination including assessment of objective cure, sling erosions and development of pelvic organ prolapse using the POP-Q system (42).

Exposure: Having had TVT-A sling operation at AHUS.

- a. *Primary outcomes:* Long-term objective cure rates.
- Objective cure will be defined as having no leakage (0 g) at a cough-jump pad weighing stress test (43).
- b. *Secondary outcomes:* The same as defined under 1) Long-term subjective outcomes.
- In addition, we will evaluate differences in the rate of mesh exposures and the development of pelvic organ prolapse (POP) using the POP-Q evaluation system (42).
- The severity of tape exposure will be evaluated using the ICS and IUGA prosthesis and graft complication classification system (44). In addition, we will evaluate the intervention for surgical complications using the Clavien-Dindo Classification (45, 46).

PhD-project, Part 3

We will study the positioning of the shorter sling TVT-A under the urethra using dynamic 2D and 3D ultrasound. We will evaluate if there is an “optimal sling placement zone” for shorter slings.

Our aim is to study the association between sling position, tension and anchoring under the urethra, and subjective and objective cure rate, and long-term complication rates, especially chronic pelvic pain.

Our null hypothesis is that there are no associations between sling position, tension or anchoring of the tape and subjective and objective outcomes including complications such as chronic pain development.

Study design: Prospective observational study

Study population: 318 women having had surgery with the intermediate sling TVT-A at AHUS between 2016 and 2020.

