Follow-up: Women who consent to study participation and attend the physical follow-up will undergo a clinical examination that includes a transperineal ultrasound (TPUS) examination in the dorsal lithotomy position using a 3,5-6 MHz curved array abdominal probe (47). The TPUS volumes and images will be obtained with an empty bladder at rest and under full Valsalva (48).

Exposure: Position, tension (shape) and anchoring of the sling, and measuring sling position in relation to well-defined anatomical markers.

- a. *Primary outcomes:* Any association between sling position, tension or anchoring and subjective and objective cure rate, complication rates and especially the development of chronic pelvic pain. For the definitions of cure rates, *see under part 2*.
- b. *Secondary outcomes:* Any association between sling position, tension or anchoring and long-term complications, especially chronic pelvic pain, *see part 2*.

Statistics, power and sample size:

PhD-project, Part 2

This is a follow-up study of all women having been operated at AHUS with SIMS Ajust or TTVT-A in the study period. Few studies with long-term outcomes after shorter slings have been published. The first part of the long-term follow-up will therefore be a prospective follow-up study with no group comparisons. For this part, power calculations are not feasible as all women having had SIMS Ajust or TTVT-A in the study period consenting to study participation will be analysed for subjective outcomes, whereas all women in the TTVT-A group consenting to study participation will be analysed for objective outcomes.

PhD-project, Part 3

For the transperineal ultrasound (TPUS) part of the project, various outcomes will be evaluated based on sub urethral sling position, tension and anchoring. As there is little scientific published data on how sling placement affect subjective and objective outcomes of sling surgeries, a pre-study sample size estimation must in part be made on best clinical guess. Based on the following assumptions:

We estimate that 80 % of the women will have the sling placed in the “optimal position” and 20 % outside the optimal position as shown in a small study published in 2017 by Hegde and co-workers (37). Therefore, the estimated group ratio will be 1:4.

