A clinically relevant effect size (group difference) regarding subjective outcomes is not established, but based on our clinical experience, we have set the minimal relevant group difference in success rate to 30 % (85 % subjectively cured in the “optimal position” group vs 55 % in the “non-optimal position group”).

With a significance level (α) of 0,05 and a statistical power (β) of 80%, the estimated sample size to be included for TPUS evaluation is 107 women (37). Even though we invite all 318 TTVT-A women to attend the physical long-term follow-up with ultrasound evaluation, realistically we estimate that only 50 % will want to participate. Even with 50 % participation we should, based on our sample size calculation, be able to draw valid conclusions.

Risk evaluation and countermeasures

The main risk to the project is patient inclusion. To get robust and valid scientific data we are depending on women being willing to participate in the project with clinical examinations and ultrasound measurements. Based on previous experience, Norwegian women usually do want to participate in long-term follow-up studies. In the 10-year follow-up study of retropubic TVTs conducted by the main supervisor [name] 89 % consented to study participation, and 60 % to a physical follow-up (6). Even a conservative estimate of 50 % would therefore be enough to draw valid conclusions. However, if less than 50 % agree to study participation, we do have the possibility to extend the study period to include women operated in 2021. According to the work plan for the PhD project (below) these women will then be evaluated in 2024 at the earliest and as such have follow-up of minimum 4 years.

User Participation

The project has two user representatives, [name] as part of NFIRs national Advisory Unit and [name] as user representative at the Women's Clinic, AHUS. They have both participated in the planning of the project and given valuable comments in developing the study protocol. Both have agreed to stay on as part of the project group. We plan on having quarterly meetings with the user representatives throughout the whole project period.

Ethical considerations

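### Part 3 makes at least nine associations primary, lists two of the outcomes again as secondary, and sizes only one association without naming it as the primary test

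*Protocol*

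**What the plan says.** In the protocol's section on Part 3, the primary outcome is "Any association between sling position, tension or anchoring and subjective and objective cure rate, complication rates and especially the development of chronic pelvic pain". The secondary outcome, on the next line, is "Any association between sling position, tension or anchoring and long-term complications, especially chronic pelvic pain". The null hypothesis in the same part is also joint: "Our null hypothesis is that there are no associations between sling position, tension or anchoring of the tape and subjective and objective outcomes", with complications such as chronic pain included.

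The sample size is in the protocol's section on statistics, power and sample size, under Part 3. It takes 80% of women inside and 20% outside the optimal position: "Therefore, the estimated group ratio will be 1:4". For subjective outcomes, "we have set the minimal relevant group difference in success rate to 30" percentage points, namely 85% cured inside against 55% outside. With alpha 0.05 and 80% power, "the estimated sample size to be included for TPUS evaluation is 107 women".

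All 318 TVT-A women are invited and half are expected to attend. The section concludes: "Even with 50 % participation we should, based on our sample size calculation, be able to draw valid conclusions". The section on risk evaluation and countermeasures repeats the thought: "Even a conservative estimate of 50 % would therefore be enough to draw valid conclusions".

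**The concern.** A primary outcome tells the reader in advance which result the study stands on. Here it is any of at least nine associations, and none is put first. Complications and chronic pelvic pain are both primary and secondary, so the protocol contradicts itself on their rank. Followed as written, any one of these associations could later be reported as the primary result.

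The sample size section does work with a single contrast, but the outcome section does not say that this contrast is the primary test. The outcome stressed most, chronic pelvic pain, is not the one that was sized. A reader of the final paper could take a null pain result to carry the planned 80% power, although no power was calculated for pain.

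**Working it through.** **1. Count of pairings.** Exposures: position, tension, anchoring (3). Outcomes: subjective cure, objective cure, complications, chronic pelvic pain. Part 2 lists prolonged pain among the complications, so there are 3 or 4 outcomes.
- 3 × 3 = 9 with pain inside complications
- 3 × 4 = 12 with pain apart

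Part 2 names several types of complication, so 9 is a minimum.

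**2. Overlap.** The secondary outcome pairs the same three exposures with complications and chronic pelvic pain. Each of these pairings is already in the primary outcome.

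**3. The protocol's own figure.** Inputs from the sample size section: 0.85 vs 0.55, ratio 1:4, alpha 0.05 (taken as two-sided, since sidedness is not stated), power 0.80. Arcsine formula:
- h = 2·asin(√0.85) − 2·asin(√0.55) = 2.346 − 1.671 = 0.675
- smaller group = (1.960 + 0.842)² × (1 + 1/4) / h² = 21.5
- total = 21.5 + 86.1 = 107.6

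This agrees with 107. Exact Fisher power is 0.782 for 21 + 86 = 107 and 0.924 for 32 + 127 = 159, where 159 is 50% of 318.

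**4. Does this power carry over to pain?** The protocol gives no pain rate, so every rate below is an assumption. Fisher power, two-sided 0.05, same 1:4 split:

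| Pain inside vs outside the zone | 107 women | 159 women |
|---|---|---|
| 5% vs 10% | 0.120 | 0.171 |
| 10% vs 20% | 0.216 | 0.312 |
| 5% vs 15% | 0.308 | 0.441 |
| 10% vs 30% | 0.561 | 0.749 |
| 5% vs 25% | 0.708 | 0.866 |
| 10% vs 40% | 0.841 | 0.956 |
| 5% vs 35% | 0.923 | 0.985 |

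Power runs from very low to higher than for the sized pairing, depending only on rates that the protocol does not state. At the expected 159 women, 80% power needs about 17%, 23% or 32% pain outside the zone if the rate inside is 2%, 5% or 10%.

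**5. Does it carry over to tension and anchoring?** No split is given for them. Keeping 85% vs 55% and assuming other splits:

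| Split | 107 women | 159 women |
|---|---|---|
| 1:9 | 0.600 | 0.746 |
| 1:1 | 0.916 | 0.985 |

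Again power may be lower or higher than for the sized pairing.

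**The case against.** Sizing a study on one contrast while examining others is ordinary in an observational cohort that invites every eligible woman. No stated figure is wrong, and the order of testing and any multiplicity method may be in a statistical analysis plan that is not shown. This stands, and the point does not rest on a missing multiplicity method. It rests on how the protocol itself ranks its outcomes.

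Two stronger readings are tempting. The first is that the protocol claims adequate power for all its primary associations when it speaks of valid conclusions. The documents do not support that. Both sentences belong to a recruitment argument (159 expected against 107 needed), and the first is expressly tied to the one-pairing calculation. Neither claims power for pain, tension or anchoring. What remains is only that neither sentence says which pairing it covers.

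The second is that the study is underpowered for chronic pain. This does not follow either. The low powers come from assumed differences of 5 to 10 points. At 30 points, the only difference the protocol calls relevant (and it does so for subjective outcomes), pain power equals or exceeds that of the sized pairing. Fisher's test is also conservative, and the protocol names no test.

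A further fair objection concerns the remedy. Background and the opening of Part 3 say that the study will itself evaluate whether an optimal zone exists for shorter slings. Naming a test of inside versus outside that zone is therefore not enough unless the zone is also fixed. Ranking pain below cure is likewise a scientific choice for the investigators. The fix allows for both.

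**Conclusion.** The point holds as a fault in how the Part 3 outcomes are ranked, and should be corrected. The primary outcome covers at least 9 pairings (12 with pain apart), complications and pain are both primary and secondary, and the one pairing that was sized is not named as the primary test. The figure of 107 is right for that pairing, with about 80% power at 107 and about 92% at 159, taking a two-sided alpha. For all other pairings power is unknown, because the protocol gives no rates for the other outcomes and no split for tension or anchoring. The pain and split figures above illustrate that dependence under assumed values and are not estimates of the study's power.

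**What to change.** 1. In the Part 3 outcomes, name position (inside vs outside the optimal zone) against subjective cure as the primary test. State that the zone is fixed before outcomes are analysed and is not derived from the same outcome data. List every other association once, as secondary, with estimates and confidence intervals, and chronic pelvic pain as the key secondary outcome. Bring the Part 3 null hypothesis into line.
2. If the investigators prefer to keep pain primary, state instead an assumed pain rate and difference, and the resulting power at 107 and 159 women.
3. In the sample size section, add that 107 women give about 80% power only for position against subjective cure at a 30-point difference (85% vs 55%, 1:4), and that the other associations were not sized. The sentence under Risk evaluation and countermeasures can refer to this.

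The changes are to protocol wording and need no extra women or measurements. The zone definition must be settled in advance. The price is that fewer associations can be called confirmatory and, unless the second option is taken, that chronic pain leaves the primary outcome.

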Most of the 39 departments offering female incontinence surgeries in Norway use traditional MUS. However, one of the largest hospitals, Akershus University hospital (AHUS), has been using shorter slings as their preferred MUS since 2009, initially SIMS Ajust and later TTVT-A. At AHUS, we therefore have a unique opportunity to study the long-term results and complication rates of shorter slings by inviting women back for a long-term follow-up after undergoing sling surgery at AHUS. In addition to quality of life, complications, and patient satisfaction, this follow-up provides the possibility of investigating sling position using 2D dynamic and 3D transperineal ultrasound (TPUS) (34-37). This innovative technique that dynamically investigates the pelvic floor and sling placement is not widely used in Norway, but is available at AHUS, which also has expertise in advanced ultrasound within the research group. How the positioning of intermediate slings under the urethra may affect long-term success rates and adverse events is largely unknown. Studies on traditional slings suggest that placement more proximal or distal to the mid-part of the urethra is associated with poorer outcomes (34-36).

Whether this is coincidental or represents an actual association between sling position and long-term success and complication rates is not established for intermediate slings. To go even further, we will evaluate if there is an “optimal sling placement zone”, particularly for shorter slings. This information is currently lacking and makes it difficult for gynaecologists evaluating patients in need of repeat surgery, due to either treatment failure or long-term complications. Understanding the biomechanical effects visualized by ultrasound of the increasingly popular shorter slings would be pioneering work and enable researchers and doctors to further develop the treatment techniques for female incontinence.

Research questions and hypotheses, theoretical approach and methodology

PhD-project, Part 2

Our over-all aim is to evaluate long-term subjective and objective outcomes of shorter slings.

Study design: Prospective observational study

1) Long-term subjective outcomes

Study population: Women treated with SIMS Ajust (n = 744) at Akershus University Hospital between 2009 and 2016 and Intermediate sling TTV-A (n= 318) at Akershus University Hospital between 2016 and 2020.

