Follow-up: Potential study participants for both groups will be identified in the local quality database for female incontinence surgery (local NFIR) at AHU S and invited to a long-term follow-up (4-14 years) with questionnaires. The following questionnaires will be sent electronically to the patients together with study invitation and consent form: The validated NFIR questionnaire, the validated Pelvic Floor Impact Questionnaire (PFIQ-7) (38, 39) as well as additional questions regarding pain (40).

- a. *Primary outcomes:* Long-term subjective cure rate.
- Long-term subjective cure is estimated by calculating a stress urinary incontinence index score (SUIS) from 4 clusters of questions measuring degree of symptom bother in the validated NFIR questionnaire, from 0 (no symptoms) to 12 (high symptom load) where a score < 3 is defined as subjective cure (41).
- b. *Secondary outcomes:* Long-term treatment satisfaction scores, quality of life score and complication rates.
- Differences in improvement of quality-of-life using a Quality-of-life index score (QoLIS) generated from 4 questions in the NFIR questionnaire measuring QoL impact. This index ranges from 0 (excellent quality of life) to 16 (poor quality of life) (41). In addition, the Pelvic Floor Impact Questionnaire (PFIQ-7) (38, 39) will be used to further evaluate the Quality-of-life impact.

- Differences in treatment satisfaction rates are defined as the percentage of women answering “very satisfied with treatment” given the options “very satisfied”, “moderately satisfied”, “neither satisfied nor dissatisfied”, “moderately dissatisfied” or “very dissatisfied” in the NFIR questionnaire.
- Differences in total complication rates (all types included), re-operation rates, vaginal tape exposure, persistent and de novo urgency incontinence and prolonged pain.
 - Persistent and de novo urgency incontinence is calculated from the NFIR questionnaire using 4 clusters of questions that generate an urgency urinary incontinence score (UUIS) quantifying the degree of urgency symptom bother from 0 (no symptoms) to 8 (high symptom load) (41). De novo urgency incontinence will be defined as having had a UUIS of ≥ 4 at the long term follow up in women who had no urgency incontinence symptoms before surgery (preoperative urgency urinary incontinence score = 0).

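### The fallback cohort operated in 2021 and seen from 2024 has about 3 years of follow-up, not the stated minimum of 4

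*Protocol*

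**What the plan says.** In Part 2 of the protocol, under long-term subjective outcomes, women in both sling groups are to be "invited to a long-term follow-up (4-14 years) with questionnaires". The study population there gives the intermediate-sling (TVT-A) group as "n= 318) at Akershus University Hospital between 2016 and 2020". The same operation years define the TVT-A women invited to the physical and ultrasound follow-up in Parts 2 and 3.

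The section Risk evaluation and countermeasures names patient inclusion as the main risk and gives one specific countermeasure. The trigger is "if less than 50 % agree to study participation", and in that case "we do have the possibility to extend the study period to include women operated in 2021". The next sentence refers to the PhD work plan for the timing and says that "these women will then be evaluated in 2024 at the earliest and as such have follow-up of minimum 4 years".

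**The concern.** The sentence supplies an operation year (2021), an earliest evaluation year (2024) and a minimum follow-up (4 years), and presents the third as a result of the other two: "as such have follow-up of minimum 4 years". The three figures do not agree.

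The stated minimum is what makes the fallback look harmless, because it implies that the added women meet the lower end of the 4-14 year range given for the main cohorts. If the extension were used in 2024, women below that lower end would enter a study presented as a follow-up of 4 years or more. The Background notes that the national registry already collects data at 3 years, though with low coverage and mostly from questionnaires. By calendar years, women operated in 2021 and seen in 2024 would be at that existing time point, not beyond it.

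**Working it through.** **Inputs**, all from the protocol:

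- Operation year of the added women: 2021 (Risk evaluation and countermeasures).
- Earliest evaluation year: "these women will then be evaluated in 2024 at the earliest".
- Stated minimum follow-up: 4 years (same sentence).
- For comparison, operation years of the defined TVT-A cohort: 2016 to 2020 (Part 2, study population).

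**Step 1. Calendar years.** Follow-up = evaluation year − operation year.

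- Operated 2021, evaluated 2024: 2024 − 2021 = 3. The stated 4 is not reproduced.
- Operated 2020, evaluated 2024: 2024 − 2020 = 4. The stated figure is obtained only with this operation year.
- Operated 2021, evaluated 2025: 2025 − 2021 = 4. Alternatively, the stated figure is obtained with this evaluation year.

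**Step 2. Exact dates, shortest follow-up.** Take the last possible operation day of the year, 31 December, and count days to three dates in 2024. Years = days / 365.25.

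| Evaluation date | Operated 31 Dec 2020 | Operated 31 Dec 2021 |
|---|---|---|
| 1 Jan 2024 | 1096 d = 3.00 y | 731 d = 2.00 y |
| 1 Jul 2024 | 1278 d = 3.50 y | 913 d = 2.50 y |
| 31 Dec 2024 | 1461 d = 4.00 y | 1096 d = 3.00 y |

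The gap between the two operation years is one year on each date.

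**Step 3. Exact dates, longest follow-up.** From 1 January 2021 to 31 December 2024 is 1460 days, or 1460 / 365.25 = 3.997 years. Four full years would need 1461 days, reached on 1 January 2025. So during 2024 the stated minimum is not reached even as a maximum.

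**Step 4. When every woman operated in 2021 has 4 years.** From 31 December 2021 to 31 December 2025 is 1461 days = 4.00 years. The individual 4-year dates therefore run through 2025, from 1 January to 31 December.

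**The case against.** Four points can be made for the plan.

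1. **The evaluation year is only a lower bound.** The women might be seen in 2025, when the calendar difference is 4. That is possible, but a minimum is set by the earliest permitted date, and the sentence draws its minimum from 2024. Later visits could lengthen follow-up without making the printed statement true.

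2. **The work plan it cites is not in the text available.** It might show that 2024, 2021 or the 4 years is the slip. This stands as a limit on what can be concluded: the protocol alone does not settle which figure is wrong. That 4 was carried over from the 2020 operation year is a plausible inference, not something the document states. The missing plan does not make the three printed figures agree.

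3. **The plan evidently counts nominal calendar years.** By exact dates, a woman operated on 31 December 2020 also falls short of 4 years until the end of 2024. This is fair, and the calendar difference of 3 against 4 is therefore the main measure. The exact-date figures only show that no other way of counting rescues the sentence.

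4. **Little depends on it.** The fallback is optional, the protocol sets no minimum follow-up as an eligibility criterion, and no outcome definition uses a 4-year threshold. The sample size of 107 does not use the figure either. Actual follow-up could presumably be computed from operation dates in the local registry database, so misreporting is not inevitable. All of this stands, and it keeps the point minor.

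**Conclusion.** The statement is wrong as written. Women operated in 2021 and evaluated in 2024 have 3 calendar years of follow-up, one fewer than stated; by exact dates the range is 2.00 to 3.997 years. The conclusion rests only on the years printed in the sentence and on reading the women concerned as those operated in 2021, which is how the text runs.

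The severity is minor. The error matters only if participation is below 50 % and the extension is used. The protocol gives no number of operations for 2021, so the number of women affected cannot be estimated.

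**What to change.** Check the sentence against the work plan and correct it in one of two ways.

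- **Keep the 4 years and move the evaluation.** State that women operated in 2021 will be evaluated after each woman's own 4-year date, which falls during 2025. The cost is a later evaluation for these women, in 2025 instead of 2024.
- **Keep 2024 and restate the minimum.** Give it as about 3 calendar years (2 to 3 years by exact dates, depending on when in 2024 the visit takes place) and describe the extended cohort accordingly. For TVT-A women operated 2016 to 2021 and seen in 2024, the calendar range is 2024 − 2021 = 3 to 2024 − 2016 = 8 years. This takes the 2021 operations to be TVT-A, the group whose defined period ends in 2020. The cost is a less favourable stated minimum, below the lower end of the range given in Part 2.

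Either way this is one corrected sentence, and the main cohort and its analysis need no change.
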